## 2 SCHEDULE OF ASSESSMENTS (SoA)

**Table 3: Schedule of Assessments**

Evaluation or Procedure	Screening Period	Treatment Period (Cycle = 28 days)												Follow-Up Period
	Screening ≤28 Days prior to D1	Cycle 1			Cycle 2		Cycle 3		Cycle 4-12	Cycle 12	Cycle 13 onwards	End of Treatment Visit (EOT) 	90-Day Safety Follow-up Visit/ End of Study Visit 	
Day	Screen	D1	D4 ±1 day	D8 ±1 day	D15 ±1 day	D1 ±1 day	D15 ±1 day	D1 ±1 day	D15 ±1 day	D1 ±2 days	D28 ±2 days	D1 ±2 days	Within 14 days after decision on treatment discontinuation	±7 days
Starting Evaluations and Eligibility														
Informed consent	X													
Inclusion/exclusion criteria	X	X 												
Demography	X													
Medical history/current medical condition	X													
Disease history/staging/Ann Arbor	X													
Disease risk assessment (IPI)	X													
Throughout Evaluations														
Prior/concomitant therapy 	X	X	X	X	X	X	X	X	X	X		X	X	X
Physical examination (F – full, L – limited)	F	L						L		L 		L 	F	
ECOG performance status	X	X 				X		X		X			X	
Body weight/height 		X	X	X	X	X	X	X	X	X		X	X	
B-symptoms	X	X				X		X		X		X	X	
Vital signs 	X	X	X	X	X	X	X	X	X	X		X	X	
12-lead resting ECG	X	X 			X 	X 		X 		X 5a			X	
Adverse events (AEs, SAEs and AESIs)	X	X	X	X	X	X	X	X	X	X		X	X	X
Laboratory														
Urinalysis (local lab)	X	X				X		X		X			X	
Pregnancy test (FCBP) 	X	X 		X 	X 	X 		X 		X 		X 	X	
Pregnancy and risks counselling	X	X				X		X		X			X	
US only: pregnancy and risk interview	X	X				X		X		X			X	
Hematology and Serum chemistry (local lab) 	X	X	X	X	X	X	X	X	X	X		X	X	
Serology Hepatitis B (local lab)	X													

Evaluation or Procedure	Screening Period	Treatment Period (Cycle = 28 days)												Follow-Up Period
	Screening ≤28 Days prior to D1	Cycle 1				Cycle 2		Cycle 3		Cycle 4-12	Cycle 12	Cycle 13 onwards	End of Treatment Visit (EOT) 	90-Day Safety Follow-up Visit/ End of Study Visit 
Day	Screen	D1	D4 ±1 day	D8 ±1 day	D15 ±1 day	D1 ±1 day	D15 ±1 day	D1 ±1 day	D15 ±1 day	D1 ±2 days	D28 ±2 days	D1 ±2 days	Within 14 days after decision on treatment discontinuation	±7 days

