From Cycle 4 onwards, blood samples for tafasitamab anti-drug antibodies (ADAs) will be collected pre-dose on D1 of every other cycle until Cycle 12, i.e. Cycle 4, Cycle 6, Cycle 8, Cycle 10, Cycle 12.

Tafasitamab PK sample will be taken pre-dose and 30 min  $\pm$  15 min after the end of tafasitamab infusion.

10aTafasitamab PK samples will be taken pre-dose and 30 min  $\pm$  15 min after the end of tafasitamab infusion on C4D1 and afterwards pre-dose on D1 of every other cycle until Cycle 12, i.e. Cycle 6, Cycle 8, Cycle 10, Cycle 12.

PET-CT or PET-MRI should be performed at screening, at C12D28 ( $\pm$  4 days) and at EOT visit unless disease progression was already radiologically confirmed prior to the EOT visit. If progression/relapse is suspected on the basis of clinical symptoms, PET-CT or PET-MRI should be performed to confirm disease progression. PET/CT or PET-MRI from Cycle 25 onwards should be performed only if deemed necessary, and not more than once per year.

11aCT or MRI should be performed within 4 days prior to C3D1, C5D1, C7D1 and C10D1. From Cycle 13-24 CT or MRI should be performed approximately every 3 months  $\pm$  2 days from the previous scan. The first assessment during this phase will take place 3 months  $\pm$  2 days after C12D28. From Cycle 25 onwards: approximately once every year  $\pm$  2 weeks from the previous scan.

Repeat bone marrow biopsy only in those patients who had known bone marrow involvement at screening to confirm a CR. If repeat bone marrow biopsy is required to confirm CR, the assessment should be done at C3D15  $\pm$  1 day and/or within 15 days after C5D1, C7D1, C10D1 and C12D28. Bone marrow assessment from Cycle 13 to 24 approximately every 3 months  $\pm$  2 weeks from the previous assessment to be performed to confirm a CR only in those patients who had known marrow involvement at screening.

Tafasitamab infusions should be given after pre-medication administration 30–120 minutes prior to starting the infusion. For patients who do not experience any grade 2 or higher IRRs with their first four infusions, pre-medication at subsequent treatments may be omitted according to institutional treatment guidelines.

Regardless of the reason for study treatment discontinuation, patients will have a safety follow-up visit or phone call scheduled 90 days after the last dose of the study treatment.

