## 5 STUDY DESIGN

### 5.1 Overall Design

MOR208C115 (MINDway) is an open-label, multi-center, phase 1b/2 study of tafasitamab combined with LEN to evaluate the safety and PK [REDACTED] in adult patients with R/R DLBCL.

Patients will receive LEN in combination with tafasitamab in 28-day cycles. [REDACTED]

Tafasitamab will be administered as intravenous infusion according to the following dosing schedule:

- [REDACTED]
- [REDACTED]
- [REDACTED]
- [REDACTED]

LEN (25 mg) will be administered for a maximum of 12 cycles or until disease progression, unacceptable toxicity, withdrawal, death or lost to follow up, whichever comes first. After cycle 12 or LEN discontinuation, patients will continue with tafasitamab monotherapy [REDACTED] until disease progression, unacceptable toxicity, withdrawal, death or lost to follow up, whichever comes first.

[REDACTED]

[REDACTED]. If a patient discontinues the study for reasons other than safety before the completion of the predefined safety observation window (5 weeks) as per [Section 8.4](#), the patient may be replaced.

[REDACTED]

A patient is considered to have started the study and entered the screening period when they have signed the informed consent form.

[REDACTED]  
[REDACTED]  
[REDACTED]. This safety window will also be maintained [REDACTED]  
[REDACTED]

Patient is considered enrolled in the study if they received at least one dose of any study treatment (tafasitamab or LEN).

The end of the study is reached for an individual patient if any of the following applies: withdrawal, lost to follow up, death or completion of the end of study (EOS)/90-Day Safety Follow-up visit after treatment discontinuation. Regardless of the reason for treatment discontinuation on study (with the exception of withdrawal of consent, death or lost to follow up) all patients must complete a Safety Follow-up visit 90 days after the last dose of study treatment, see [Section 2](#).

The end of the study is reached when all patients still on study treatment have been followed for at least 3 years, or when the final patient on study has completed their last visit, whichever comes first.

Patients who are receiving ongoing treatment at the end of study may continue treatment with either of the options below upon assessment of a clinical benefit of continued treatment by the investigator and in accordance with the local regulatory guidance:

- commercially available tafasitamab for the approved dose regimen locally; or

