## 7.12 Treatment After the End of the Study

If the study is terminated early by the Sponsor for reasons other than safety, alternative methods of drug supply may be considered for patients that are benefitting from treatment, in accordance with local regulatory guidance.

The Sponsor does not have any plans to provide study treatment to patients after the end of the study.

**End of Study:** The end of the study is reached when all patients still on study treatment have been followed for at least 3 years, or when the final patient on study has completed their last visit, whichever comes first.

Patients who are receiving ongoing treatment at the end of study may continue treatment with either of the options below upon assessment of a clinical benefit of continued treatment by the investigator and in accordance with the local regulatory guidance:

- commercially available tafasitamab for the approved dose regimen locally; or
- participation in the tafasitamab extension study if above option is not available

**End of study visit for a patient:** An end of study visit for a patient is defined as the visit taking place when the patient has completed 90-day safety follow up after the last tafasitamab dose given.

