### 12.3 Appendix 3: Study Specific Definitions

For the purposes of this protocol, **primary refractory disease** is defined as a disease progressing in the course of the first line treatment as per International Working Group response criteria (Cheson *et al.*, 2007), and/or, showing a response of less than a PR to first-line treatment or disease recurrence/progression within  $\leq 6$  months from the completion of first-line therapy.

**Disease refractory to last treatment** is defined as having had less than a PR to the most recently administered systemic therapy.

**Relapsed/progressive/recurrent disease** reflects the appearance of any new lesions or increase by  $\geq 50\%$  of previously involved sites from nadir according to the International Working Group response criteria (Cheson *et al.*, 2007), after the most recent systemic therapy.

**First act of recruitment (EU):** For purposes of EU clinical trial regulation (536/2014) the first act of recruitment of a potential patient is defined as the date of initiation of the first site.

**Start of study:** A patient is considered to have started the study and entered the screening period when they have signed the informed consent form.

**End of Treatment:** The end of treatment is defined as the date when the patient has received last tafasitamab dose. An end of treatment visit will be performed within 14 days after decision on treatment discontinuation.

**End of Study:** The end of the study is reached when all patients still on study treatment have been followed for at least 3 years, or when the final patient on study has completed their last visit, whichever comes first.

Patients who are receiving ongoing treatment at the end of study may continue treatment with either of the options below upon assessment of a clinical benefit of continued treatment by the investigator and in accordance with the local regulatory guidance:

- commercially available tafasitamab for the approved dose regimen locally; or
- participation in the tafasitamab extension study if above option is not available

**End of study visit for a patient:** An end of study visit for a patient is defined as when the patient has completed 90 day safety follow up after the last tafasitamab dose given.

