3. STUDY DESIGN

MOR208C115 (MINDway) is an open-label, multicenter, Phase 1b/2 study of tafasitamab combined with LEN to evaluate the safety and PK of tafasitamab tafasitamab in adult participants with R/R DLBCL.
Participants will receive LEN in combination with tafasitamab in 28-day cycles.
•
Lenalidomide 25 mg will be administered for a maximum of 12 cycles or until disease progression, unacceptable toxicity, withdrawal, death, or lost to follow-up, whichever occurs first. After Cycle 12 or LEN discontinuation, participants will continue with tafasitamab monotherapy until disease progression, unacceptable toxicity, withdrawal, death, or lost to follow-up, whichever occurs first.
participant discontinues the study for reasons other than safety before completion of the predefined safety observation window (5 weeks), the participant may be replaced.

A participant is considered to have started the study and entered the screening period when they have signed the ICF.

A participant is considered enrolled in the study if they receive at least 1 dose of study drug (tafasitamab or LEN).

The EOS is reached for an individual participant if any of the following applies: withdrawal, lost to follow-up, death, or completion of the EOS/90-day safety follow-up visit after treatment discontinuation. Regardless of the reason for treatment discontinuation (with the exception of withdrawal of consent, death, or lost to follow-up) all participants must complete a safety follow-up visit 90 days after the last dose of study treatment.

The EOS is reached when all participants still receiving study treatment have been followed for at least 3 years, or when the final participant on study has completed their last visit, whichever occurs first.

Overall survival follow-up after EOT will not be performed in the study.

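### Three Protocol definitions time the end-of-study visit, where AE recording stops, from the last tafasitamab dose; the rest of the plan and the TEAE window use the last dose of either drug

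*Protocol*

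**What the plan says.** **Tafasitamab as the starting point.** The Synopsis and Section 7.12 of the Protocol define the patient's end-of-study visit as taking place "when the patient has completed 90-day safety follow up after the last tafasitamab dose given". Appendix 3 repeats this: "when the patient has completed 90 day safety follow up after the last tafasitamab dose given". Appendix 3 also ties end of treatment (EOT) to that drug: "The end of treatment is defined as the date when the patient has received last tafasitamab dose". SAP 4.2.3 defines EOT in the same way.

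**Study treatment as the starting point.** Table 3 of the Protocol has a single column for the visit, headed "90-Day Safety Follow-up Visit/ End of Study Visit", with a tolerance of ±7 days. Footnote 14 says that "patients will have a safety follow-up visit or phone call scheduled 90 days after the last dose of the study treatment". Section 5.1 says that "all patients must complete a Safety Follow-up visit 90 days after the last dose of study treatment", and SAP Section 3 that "all participants must complete a safety follow-up visit 90 days after the last dose of study treatment". SAP 4.2.5 defines the last date of study treatment as the last non-zero dose of either component.

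**What depends on the visit.** Under Protocol 9.4.7.1, AEs, SAEs and AESIs are entered in the eCRF up to the end-of-study visit. After that, the investigator must notify only SAEs and AESIs judged reasonably related. The primary estimand, Protocol 10.3.7.1 and SAP 10.2.1.3 all run the TEAE window to 90 days after the last dose of study treatment.

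**Deaths.** SAP 10.2.3 calls a death on-treatment if it comes after the first dose and before the last dose. It joins last dose of study treatment and EOT with a slash, as if they were one date.

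**The concern.** Incidence and severity of TEAEs is the primary endpoint. If recording ends 90 days after the last tafasitamab dose but the window closes 90 days after a later LEN dose, the end of the window is unobserved. New non-serious events, and serious events judged unrelated, would then be missed.

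LEN can be the last drug given. Protocol 7.3.1.3 and 7.3.1.4 allow LEN to continue when an infusion reaction or cytokine release syndrome rules out more tafasitamab. SAP 6.2.2 counts patients ongoing on LEN only. A rare toxicity is not needed. Table 3 states that "CT or MRI should be performed within 4 days prior to C3D1, C5D1, C7D1 and C10D1". A patient who stops both drugs at the scan before C5D1, C7D1 or C10D1 may have had the last infusion on Day 1 of the preceding cycle and LEN through Day 21.

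The SAP carries the mixed wording further. SAP 10.2.1.4 counts 90 days from end of treatment, so an AE could carry both that label and the TEAE label.

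**Working it through.** No sample size or test is involved. The check compares the definitions and counts days.

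**Inputs**
- Follow-up of 90 days, visit tolerance ±7 days: Protocol Table 3 and its footnote 14.
- LEN on Days 1 to 21 of a 28-day cycle, at most 12 cycles: Protocol 7.3.2.
- Last date of study treatment is the later drug: SAP 4.2.5.
- Infusions on Day 1 only from Cycle 4: an assumption. The dosing table is redacted. Table 3 shows only Day 1 dosing visits from Cycle 4, and SAP 6.4.2.4.3 changes the infusion rate between Cycle 3 Day 15 and Cycle 4 Day 1; both fit the assumption.

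**Formula.** Gap = last LEN date − last tafasitamab date. This is how much earlier the tafasitamab-based visit falls, and the part of the window lost if that visit is on time.

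**The SAP's own example (4.2.5).** Last tafasitamab is 13 APR 2022 and last LEN is 20 APR 2022, so the last date of study treatment is 20 APR 2022. Adding 90 days gives 12 JUL 2022 from tafasitamab and 19 JUL 2022 from study treatment. The gap is 7 days.

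**Other cases**
- Last infusion Day 15, LEN to Day 21: 21 − 15 = 6 days.
- Last infusion Day 1, LEN to Day 21: 21 − 1 = 20 days, and 20/90 = 22% of the follow-up period.
- Each further LEN-only cycle adds 28 days.

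For gaps of 6 and 7 days the window closes 96 and 97 days after the last tafasitamab dose. A tafasitamab-based visit on its latest permitted day (90 + 7 = 97) still covers it.

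**The 20-day case across the tolerance.** Days are counted from the last tafasitamab dose; the TEAE window closes on day 90 + 20 = 110.

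| Visit | Tafasitamab-based: day (days missed) | Study-treatment-based: day (days missed) | Missed because of the definition |
|---|---|---|---|
| 7 days early | 83 (27) | 103 (7) | 20 |
| On time | 90 (20) | 110 (0) | 20 |
| 7 days late | 97 (13) | 117 (0) | 13 |

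The definition moves the visit by 20 days in every row.

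**Deaths.** No patient can die before a dose actually received. This holds for the last tafasitamab date and for the last date of either drug. The on-treatment category in SAP 10.2.3 is therefore empty under both readings. It is nevertheless summarised for the SAF, PAS and ENR (SAP 10.2.4.1.2 and 10.2.4.2.1; Appendix A, Table 3.2.24.1.x).

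**The case against.** The strongest reply is that the Protocol already settles which rule a site follows. Section 9 makes adherence to the SoA mandatory, Sections 8.1 and 8.2 send sites there for follow-up data, and footnote 14 uses study treatment. Section 10.3.7.1 equates the end of the 90 days after study treatment with the end of the study. The three outlying sentences are definitions, not scheduling instructions. This stands, and it limits the point to a consistency error with a possible effect on data.

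Several stronger readings are tempting, and the documents do not support them:

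- *Primary-endpoint data will be lost.* This would require a site to set aside the SoA for a patient whose last drug is LEN.
- *A site that follows the SoA loses nothing.* A visit 7 days early misses up to 7 days under that rule too.
- *The 20-day case costs 13 to 27 days.* That range mixes visit tolerance with the error in the definition; 7 of the 27 days would be missed under the SoA as well.
- *The gap could reach 328 days* (tafasitamab stopped after C1D1, LEN to C12D21: 11 × 28 + 21 − 1). Section 7.3.1 stops both study drugs when two consecutive tafasitamab doses are skipped in Cycles 1 to 3. The text does not say whether a permanent stop after a reaction counts as skipping, so 328 days cannot be taken as the size.
- *The choice of date in SAP 10.2.3 moves deaths between categories.* It moves none, since the on-treatment category is empty under either date. The missing day count is a separate defect.
- *SAP 10.2.1.4 changes TEAE counts.* No planned output uses its label; the tables follow 10.2.1.3.

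**Conclusion.** The conflict is real and stands in current, unredacted text. The definitions based on tafasitamab are the outliers, because the SoA, Section 5.1, SAP Section 3 and every statement of the TEAE window use study treatment.

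Its effect is conditional on a site applying an outlying definition to a patient whose LEN outlasted tafasitamab. The number of such patients is unknown and may be zero. For an on-time visit the loss is 6 to 7 days in the simple cases, which the visit tolerance can absorb. It is 20 days in the Day 1 case, which rests on the inferred infusion schedule. It is longer with LEN-only cycles, subject to the Cycle 1 to 3 stopping rule. For patients who go on to tafasitamab alone the two dates coincide.

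The empty on-treatment death category is a separate SAP defect and does not depend on what sites do.

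**What to change.** 1. **Protocol Synopsis, Section 7.12 and Appendix 3:** count the 90 days from the last dose of either study drug (tafasitamab or LEN, whichever is later).
2. **SAP 10.2.1.4:** refer to the last date of study treatment (SAP 4.2.5). This is for consistency only.
3. **Clinical study report:** state how many patients had their end-of-study visit less than 83 days (90 − 7) after their last LEN dose, leaving out deaths, withdrawals and losses to follow-up. This shows whether early visits occurred, even if the Protocol is not amended again.
4. **SAP 10.2.3:** define on-treatment death as death from the first dose to a prespecified number of days after the last date of study treatment (SAP 4.2.5), and post-treatment death as anything later. One cycle, 28 days, is an example; the number is the sponsor's choice.

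The cost is one phrase in three Protocol places and edits to two short SAP sections. Patients whose LEN outlasts tafasitamab, at any site that had used the tafasitamab rule, would have a somewhat later contact, which footnote 14 allows by phone.

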## 8 PATIENT DISCONTINUATION

### 8.1 Discontinuation From the Study

A patient may withdraw from participation in the study at any time at his/her own request or may be removed at any time at the discretion of the investigator for safety, behavioral, compliance, or administrative reasons. If such premature discontinuation occurs, the investigator should determine the primary reason for a patient's premature discontinuation from the study and record the information in the eCRF. If the reason for premature discontinuation is an adverse event, monitoring should continue until the outcome is evident, unless the patient has withdrawn his/her consent to study participation.

If the patient withdraws consent, the sponsor may retain and continue to use any data collected before such a withdrawal of consent.

If a patient withdraws from the study, he/she may request destruction of any samples taken and not tested, and the investigator must document this in the site study records and eCRF.

See SoA ([Section 2](#)) for data to be collected at the time of study discontinuation and follow-up and for any further evaluations that need to be completed.

### 8.2 Discontinuation of Study Treatment

Study treatment must be discontinued for a patient under the following circumstances:

- Pregnancy or expressed intent to become pregnant
- Disease progression
- Withdrawal of consent
- Use of prohibited treatment, including participation in another interventional study and/or initiation of new anti-cancer treatment (see [Section 7.9](#) for details)
- Unacceptable toxicity or TEAE, as determined by the investigator
- Protocol Deviation that may impact the benefit/risk assessment for the individual patient following discussion with the Medical Monitor
- Occurrence of new diseases that could influence the treatment efficacy, for which the study medications are contraindicated or that are treated with a medication that is not permitted as a concomitant medication
- Any other medical condition that may jeopardize the patient's safety if he or she continues on study treatment

The investigator is encouraged to keep a patient experiencing clinical benefit on study treatment per investigator discretion unless significant toxicity puts the patient at risk or repeated cases of routine noncompliance put the study outcomes at risk.

An End of Treatment visit must be performed within 14 days after decision on treatment discontinuation. See the SoA ([Section 2](#)) for data to be collected at the time of treatment discontinuation and follow-up and for any further evaluations that need to be completed.

Patients who are withdrawn for any reason may not re-enter this clinical study at any time.

